- 1391 Psychological discomfort during study procedures (i.e., during study assessments). With regard to participants' psychological discomfort and overall well-being, we noted above that 1392 the interviewers will be specifically trained to be sensitive to subjects discomfort and 1393 1394 concerns. These issues will be of central focus during their training. If a participant finds the research procedures to be upsetting or aversive, he/she will have the option to withdraw from 1395 the study. We will refer participants to an appropriate clinical setting for evaluation and/or 1396 1397 treatment (a) in the unlikely event that an interviewer judges a participant to immediately require such care for psychological distress, or (b) if the participant him- or herself inquires 1398 1399 about receiving such care. The criteria for establishing that a participant immediately 1400 requires care are that the participant expresses thoughts or an intention to harm him/herself or 1401 others. During the HROOL assessment interviewers will be alert for any statements volunteered by the participant regarding thoughts or intent for harm or for the participant's 1402 1403 affirmative response to the PRIME-MD items that refer to thoughts or intent of harming self or others. In this situation, confidentiality would have to be broken in order to protect the 1404 1405 participant. The participant will be made aware of this contingency in the informed consent form. If this circumstance arises, the interviewer will initially consult the specific center 1406 study coordinator to arrange for an evaluation at the respective institute, or at a local facility 1407 in the geographical area where the participant resides if he/she lives a long distance from the 1408 1409 living donor transplant program and prefers a local referral. This approach meets IRB 1410 guidelines, and these procedures have successfully facilitated such local and long-distance arrangements in our past studies. We have had to invoke these procedures with any 1411 1412 transplant-related population extremely rarely.
- 1413 **5.1.4 Unauthorized data release**

1414 **5.1.4.1 Core Protocol**

The data sets will be stored on a secure server with restricted access (requires a unique username and 1415 1416 password) at the DCC and every precaution will be taken to keep the information private. However, there is always the possibility of unauthorized release of data about subjects. Such disclosure would 1417 1418 be extremely unlikely to involve a threat to life, health, or safety, since the only PHI that will be 1419 collected is month and year of birth. It is conceivable that such disclosure could have psychological, 1420 social, or legal effects on the patient. Using the standard security procedures (described above under 1421 patient confidentiality) can effectively minimize the risk of unauthorized disclosure of data. All 1422 study personnel who have access to patient data will be educated regarding the need to protect 1423 confidentiality and the procedures to be followed to ensure such protection. All staff will also be 1424 required to sign a standard medical record confidentiality agreement. The computer system on which 1425 data are maintained uses standard password protection procedures to limit access to authorized users.

1426 5.1.4.2 HRQOL Substudy

1427 The protection of study participant privacy is especially important as it relates to access and 1428 transmission of research data. We will take the following steps to assure the confidentiality of 1429 research data during storage and transmission via the internet. First, participants' names and 1430 identifying information will not be transmitted with study assessment information. Instead, an identification number will be used for data transmittal. Secondly for the handling and transmittal of 1431 1432 data, the centralized survey research centers will provide computer and web page security and data 1433 transmission between their web servers to World Wide Web users and thus provide secure 1434 transmission of data to the DCC (using such protections as Secure Sockets Layer (SSL), SSL 1435 Certificate authentication, data encryption and password protection). Each individual needing to 1436 access the web sites will be provided with a unique Username and a Password.

1437 At the survey research center responsible for data collection from a given participant, only the PI and

1438 authorized study staff will be allowed access to participant information and all computerized data

1439 will be password protected. In addition, the center will monitor individuals who are accessing

1440 participant information to assure that strict authorized access only is maintained. At the individual

1441 A2ALL sites responsible for enrolling study participants, similar procedures will be used to ensure

1442 that informed consent forms are maintained (e.g., locked files accessible only to authorized study staff).

- 1443
- 1444 5.1.5 Adverse event monitoring and reporting

1445 5.1.5.1 Definition of adverse event

1446 An adverse event (AE) is any untoward medical occurrence or unfavorable and unintended sign in a 1447 research subject that occurs during or as a result of a research procedure.

1448 For this observational study, the majority of the procedures are standard clinical care and adverse

1449 effects of clinical care will be tracked as complications but will not be considered adverse study

1450 events. Each center will review the list of study procedures and identify the specific procedures that

1451 are not standard-of-care at their institution and these will be considered research procedures.

1452 Complications that are a result of research procedures will be reported and tracked as adverse events.

1453 5.1.5.2 Assessment of event severity and relationship to treatment

1454 The modified World Health Organization (WHO) grading system will be used for grading severity

1455 of AEs (Appendix C). For AEs not covered by the modified WHO grading system, the following

1456 definitions will be used:

Mild:	awareness of sign, symptom, or event, but easily tolerated
Moderate:	discomfort enough to cause interference with usual activity and may warrant intervention
Severe:	incapacitating with inability to do usual activities or significantly affects clinical status, and warrants intervention

Life-threatening:	immediate risk of death
-------------------	-------------------------

The investigator must also assess the relationship of any adverse event to the research procedure,based on available information, using the following guidelines:

Unlikely related:	no temporal association, or the cause of the event has been identified; or the procedure cannot be implicated
Possibly related:	temporal association, but other etiologies are likely to be the cause; however, involvement of the procedure cannot be excluded
Probably related:	temporal association; other etiologies are possible, but unlikely

1459 5.1.5.3 Definition of serious adverse events

- 1460 A serious adverse event (SAE) is any adverse experience that results in any of the following outcomes:
- 1461 Death;
- Life-threatening AE (i.e., one that places the subject, in the view of the investigator, at immediate risk of death from the AE as it occurs);
- Persistent or significant disability/incapacity;
- Required in-patient hospitalization, or prolonged hospitalization;
- Congenital anomaly or birth defect.
- Additionally, important medical events that may not result in death, be life-threatening, or require hospitalization may be considered a serious adverse event when, if based upon appropriate medical judgment, they may jeopardize the subject and may require medical or surgical intervention to
- 1470 prevent one of the outcomes listed in this definition.

1471 **5.1.5.4 Reporting responsibility**

- 1472 All adverse events must be recorded. The onset and end dates, severity and relationship to study 1473 procedure(s) will be recorded for each adverse event. Any action or outcome (e.g., hospitalization, 1474 additional therapy, etc.) will also be recorded for each adverse event. Subjects will be questioned 1475 and/or examined by the investigator or his/her designee for evidence of adverse events.
- 1476
- 1477 All AEs and SAEs must be reported by the investigator to the A2ALL Data Coordinating Center
- 1478 (DCC). The DCC will review reports of all related SAEs and other relevant information
- 1479 immediately, and may request additional information from sites for analysis of these events. Sites
- 1480 will report serious adverse events according to the time frames outlined below.
- 1481 All events that are serious and related (possibly or probably) must be reported to the DCC within 24
- 1482 hours of the investigator being informed of the event. Follow-up information about a previously
- reported serious and related adverse event may be reported to the DCC within 7 working days of the
- 1484 investigator receiving the information; however, important follow-up information must be submitted

within 24 hours. All deaths connected to a study procedure must be reported to the DCC within 24hours of the investigator being informed of the event.

1487 **5.2 Benefits to the patients**

1488 There are no direct benefits to the patients for participation in the study.

1489 **5.3 Inclusion of women**

1490 This is a multi-center study drawing on a clinical population from nine transplant institutions across 1491 the United States and Canada. The demographics of the study population are pre-determined due to 1492 the all-inclusive nature of the study. Women will be included in the study as living liver donors or 1493 as recipients. It is anticipated that the representation of women will correspond to the fraction of 1494 females in the living liver donor and recipient population.

1495 **5.4 Inclusion of minorities**

1496 This is a multi-center study drawing on a clinical population from nine transplant institutions across

the United States and Canada. The demographics of the study population are pre-determined due to

the all-inclusive nature of the study. Racial and ethnic minority groups will be included in the donor and recipient components of the study and will be proportional to their representation in the living

1500 liver donor and recipient population.

1501 5.5 Inclusion of children

The study specifically excludes children. By definition this study is designed to examine the risks,
benefits and outcomes of Adult-to-Adult living donor liver transplantation. However, eligible
subjects between the age of 18 and 21 years will be enrolled.

1505 **5.6 Data and safety monitoring plan**

Accepted principles of data and safety monitoring will be observed throughout the conduct of the
A2ALL study. The NIH will appoint an independent Data Safety and Monitoring Board (DSMB)
that will provide study oversight. The DSMB will approve the study protocol prior to enrollment
and will also approve all subsequent protocol revisions.

- 1510 Each transplant center principal investigator will be responsible for monitoring the enrollment of
- 1511 subjects and submission of data to the DCC. The DCC will be responsible for monitoring for
- 1512 effective conduct of the protocol and accurate and timely data submission.
- 1513 IRBs will be provided feedback on a regular basis.
- 1514 Training of study coordinators and study monitoring activities will be conducted by the DCC to
- 1515 ensure patient confidentiality and privacy and to maximize the reliability, accuracy, and timeliness
- 1516 of study data.
- 1517 The HRQOL substudy committee and relevant survey research center staff will conduct quarterly
- 1518 meetings to review recruitment/enrollment progress, data collection activities, review participant
- 1519 complaints and any adverse events (see adverse event procedures above). As a part of these
- 1520 meetings the centralized survey research centers will generate quarterly reports to the HRQOL

- 1521 substudy committee on the tracking and management of all substudy participants. In particular, the
- 1522 centralized survey research centers report monthly retention rates, outstanding interviews/surveys,
- and data entry progress. The centers will use electronic tracking systems to monitor numbers of
- 1524 interviews scheduled, completed, refused, pending, etc. Data will be routinely exported from the
- 1525 system, examined for accuracy and completeness, and backed up to secure storage devices. Upon
- 1526 completion of data collection, final processing and cleaning of data will be conducted. A technical
- 1527 report detailing specific project methodology, response rates, and other details will be produced.
- 1528 The HRQOL substudy committee will supervise these activities and provide additional assistance as
- 1529 may be required.
- 1530 **5.7 Study organization**

1531 5.7.1 Clinical transplant centers

- 1532 The participating Clinical Centers will have primary responsibility for developing the study protocol,
- maintaining high rates of follow-up and data collection, obtaining data of high quality, and
- 1534 interpreting, presenting, and publishing findings from the study.
- 1535 Columbia University Medical Center
- 1536 New York, NY
- 1537 Principal Investigator: [name] (Steering Committee Co-Chair)
- 1538 Northwestern University
- 1539 Chicago, IL
- 1540 Principal Investigator: [name]
- 1541 University of Pennsylvania
- 1542 Philadelphia, PA
- 1543 Principal Investigator: [name]
- 1544 University of Colorado Denver
- 1545 Aurora, CO
- 1546 Principal Investigator: [name]
- 1547 University of California, San Francisco
- 1548 San Francisco, CA
- 1549 Principal Investigator: [name]
- 1550 Virginia Commonwealth University Medical College of Virginia1551 Richmond, VA
- 1552 Principal Investigator: [name]
- 1553 Lahey Clinic
- 1554 Burlington, MA
- 1555 Principal Investigator: [name]

- 1556 University of Pittsburgh Medical Center
- 1557 Pittsburgh, PA
- 1558 Principal Investigator: [name]
- 1559 University of Toronto
- 1560 Toronto, Canada
- 1561 Principal Investigator: [name]

1562 5.7.2 Data coordinating center

1563 The Data Coordinating Center (DCC) contributes content area expertise and shares in scientific 1564 leadership of the research group. The DCC has developed a communication infrastructure that includes meetings, teleconferences, electronic mail and bulletins, interactive web-based encounters 1565 and written correspondence. The DCC assists in protocol development and preparation of scientific 1566 1567 publications. The DCC has the major responsibility of creating a database and data collection 1568 systems for the transplant centers, ongoing evaluation of data quality and performance monitoring of 1569 the transplant centers and statistical analyses of the data. The DCC will also create a comprehensive 1570 Manual of Operations (MOO) that will govern the conduct of the study. The manual will detail the 1571 protocols, protocol clarifications and amendments, summary of the regulatory requirements for the 1572 study, instructions for enrollment, data collection, data management, visit schedules and detailed 1573 instructions on the use of the electronic data submission. The DCC is responsible for clinical

- 1574 monitoring of the study.
- 1575 University of Michigan
- 1576 Ann Arbor, MI

1577 Principal Investigator: [name] (Steering Committee Chair)

1578 5.7.3 Steering committee

1579 The primary governing body of the study is the Steering Committee, comprised of each of the 1580 Principal Investigators of the transplant centers, the Principal Investigator of the DCC and the 1581 NIDDK Project Officers. The Steering Committee develops policies for the study pertaining to 1582 access to patient data and specimens, ancillary studies, performance standards, and publications and 1583 presentations. They develop the study protocol and meet to discuss the progress of the study and to 1584 consider problems arising during its conduct. The Steering Committee may establish subcommittees 1585 to further develop specific components of the study protocol and propose ancillary areas of study. 1586 Small working groups may be established to prepare manuscripts and presentations.

1587

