- 343 findings cannot be compared with other centers because there is no standardized means to measure
- 344 outcome. Thus, there is no method to conduct quality improvement for postoperative live donor pain management. 345
- The American Pain Society recently issued a Patient Outcome Questionnaire-revised (APS-POQ-R) 346
- that was validated to measure patient satisfaction⁷⁷. The APS-POQ-R identified specific features of 347
- pain management that predict patient satisfaction⁷⁷. These include: ongoing assessment, 348
- interdisciplinary collaborative care that includes patient input and treatment that is efficacious, cost 349
- conscious and culturally appropriate. These features are incorporated into the questions used to 350
- 351 measure quality indicators. These characteristics are consistent with the concept of quality that
- 352 encompasses the structure, process and outcome of pain management.
- 353 The revised tool for pain assessment is inclusive. It measures outcome as patient satisfaction. A low
- pain score (little reported pain) did not guarantee that patients were satisfied with their care⁷⁷. 354
- 355 Rather, patient satisfaction (outcome) was highly influenced by interactions with the care providers;
- 356 the resources available at each site and the nature of the interactions.
- 357 The APS-POQ-R collects data about side effects, but does not collect information about more
- 358 serious complications that could be related to pain management. For example, pneumonia may
- 359 occur more frequently in patients who experience poor pain relief or have a high degree of sedation⁷⁸. Additional information is needed to fully examine the relationship between pain
- 360
- management and outcome. 361
- 362 Postoperative pain management in live donors can be significantly improved if efficacy is measured in a consistent way. This can be done by using a single set of validated tools to measure the safety 363 364 and quality of pain control in a multi-institutional study cohort. This should generate findings that 365 can be generalized to other clinical settings. The data can be used to set quality-based goals for pain management in all live liver donors. The APS-POQ-R meets the stringent criteria needed to evaluate 366
- outcome and the A2ALL Consortium already has a uniform assessment tool to measure 367
- 368 complications.

369 3 Specific Aims/Study Objectives/Hypotheses

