1264 4.6.1.7 Statistical Analysis

- 1265 Retrospective Component:
- 1266 The methods and personnel that each center uses to manage postoperative pain in live liver donors
- 1267 and methods they have stopped using, will be presented using descriptive statistics. If possible,
- 1268 graphical methods will be used to display the changes over time.

1269 The medical specialty of care providers responsible for pain management and assessment will also

- be described for the 9 A2ALL centers. This summary will include both the type of specialists
 involved, and whether pain management involved an Acute Pain Team or not. Both the proportion
- 1271 of centers with Acute Pain Teams and the composition of these teams will be described. The
- 1273 continuity of pain management through phases of patient locations (e.g., ICU, surgical ward) will
- 1274 also be reported. Finally, the opinion of the medical care providers on the adequacy of pain control
- 1275 at their center will be described, and will also be compared to patient reports at that center (using
- 1276 data from prospective component of the study).
- 1277 Prospective Component:
- 1278 Satisfaction will be assessed using (a) the single question (P9), measuring overall satisfaction, and
- (b) the individual items of the pain questionnaire (P1-P8 and P10-12). These outcomes will be

1280 presented using descriptive statistics, including frequencies, means and standard deviations.

1281 Histograms and/or boxplots will be used to identify the forms of the distributions and to identify

- 1282 outliers. Aspects of care with low scores or a large standard deviation will be identified as practices
- 1283 that require overall improvement. Boxplots and analysis of variance will also be used to display and
- 1284 compare quality indicators from the APS-POQ-R measures by center.
- 1285 To identify aspects of care that account for differences in patient satisfaction, we will evaluate 1286 predictors of overall satisfaction (P9) using linear regression. Predictors of overall satisfaction to be
- 1287 tested will include the pain relief variables (P1-P7), participation in decisions about pain treatment
- 1288 (P8), helpfulness of information received (P10), non-medicine methods of treatment (P11, P12),
- 1289 demographic variables, and donor relationship.
- 1290 The complications outcomes (P6) will be analyzed using descriptive statistics as described above.

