8.6 APPENDIX F: Prospective Living Donor Pain Survey

Name of Person Administering Survey			A2	ALL		Subjec	t ID D		
	A	2ALL	. Don	or Pa	ain S	Survey	y [PRINT FORM	
Date of First Attempt Sedation Score 0 = Fully Awake		of self/surrou	Time) AM) PM	Type of Pain M	Manageme Iral hecal	nt (check all that	apply)
2 = Moderate seda	ation, slightly	aware of self/s	surrounds. Soi	mnolent but	easily	Local	Infiltration	1	
\bigcirc 3 = Deeply sedate	d, unaware of nesia, patient i	self/surroundi s unconscious	ings.						
Date of Second Att	empt		Time		O AM	Sedation Sco	re		
P1. On this sca	e, please i	ndicate th	e least pa	iin you ha	ad in the	FIRST 24 h	nours .	11	
0 1 O O	2	3	4	5	6	7 8		9 10 O O	
No Pain	μ							Worst	Possible Pain
P1A. On this sca	le, please	indicate th	ne least p	ain you h	ad in the	e LAST 24 l	nours.		
0 1 O O	2	3	4	5	6	7 8		9 10 O O	
No Pain	J]]]]		Pos	Worst sible Pain
P2. On this sca	P2. On this scale, please indicate the worst pain you had in the LAST 24 hours .								
0 1 • •	2	3	4	5	6 〇	7 8 O (9 10 O	
No Pain								Pos	Worst sible Pain
P3. What perce	ntage of t	ime in the	LAST 24	hours we	ere you ii	n severe p	ain?		
00/	2004	2001	1001		600/				

0%	10%	20%	30%	40%	50%	60%	70%	80%	90%	100%
0	0	0	0	0	0	\bigcirc	0	\bigcirc	0	0
Never in		1-		2	1				A	lways in
severe pain									S	evere pain

							Subj	ect ID D		
P4. Choose the one number below that best describes how much pain interfered or prevented you from:										
a. Doi	ng activiti	es in bea s	uch as turr	ling, sitting	g up, repos	sitioning:	1		1	
0	1	2	3	4	5	6	7	8	9	10
O Does not					\bigcirc			\bigcirc		Completely
interfere										interferes
b. Doing activities out of bed such as walking, sitting in a chair, standing at the sink:										
0	1	2	3	4	5	6	7	8	9	10
0	0	0	0	0	0	0	0	\bigcirc	0	0
Does not interfere										Completely interferes
с. Fal	ling asleep):	ſ	1	1	1	í	1	[
0	1	2	3	4	5	6	7	8	9	10
O Doos not	0	0	\bigcirc	\bigcirc	0	0	\bigcirc	0	0	Completely
interfere										interferes
d Sto	wina aslee	n.								
u. 50		P•	2	4	F	G	7	0	0	10
0		2	5	4	5	0		8	9	
Does not										Completely
interfere										interferes
P5. Pain o On this so	can affect o	our mood a	nd emotio	ns. her that he	st shows h	now much	the nain ha	as caused y	vou to feel·	
	ale, picase	choose the			250 5110 005 1	low mach	the pulling	is caused y		
a. Anxiou	S				_		1_			
0	1	2	3	4	5	6	7	8	9	10
O Not at all					\bigcirc			\bigcirc		Extremely

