										Extremely
b. Depres	ssed									
0	1	2	3	4	5	6	7	8	9	10
0	\bigcirc	0	\bigcirc	\bigcirc	\bigcirc	0	\bigcirc	\bigcirc	0	\bigcirc
Not at all										Extremely
c. Frightened										
0	1	2	3	4	5	6	7	8	9	10
0	\bigcirc	0	0	0	\bigcirc	0	\bigcirc	\bigcirc	0	0
Not at all										Extremely

							:	Subject ID	D	
P5. (C	Cont'd)									
On thi	is scale, p	lease cho	ose the c	one num	ber that l	best show	/s how m	uch pain	caused y	ou to feel:
d. Help	oless			11			1			
0	1	2	3	4	5	6	7	8	9	10
		\bigcirc	\bigcirc	\bigcirc	0	0	0	0	0	Extromoly
NOLALA	II									Extremely
P6. Ha	ve you had	any of the	following	side effec	ts?	h a at ah aw		ity of oo ch		
Please	cnoose u	If no; if yes	s, choose t	ine one nu	imper that	best snow	s the sever	ity of each	:	
a. Naus	sea	1	1	1			1	1	1	1
0	1	2	3	4	5	6	7	8	9	10
Nono	0	\bigcirc	\bigcirc	\bigcirc	0	0	0	0	0	C Sovero
None										Jevele
b. Drov	vsiness									
0	1	2	3	4	5	6	7	8	9	10
\bigcirc	\bigcirc	\bigcirc	\bigcirc	\bigcirc	\bigcirc	\bigcirc	\bigcirc	\bigcirc	\bigcirc	\bigcirc
None										Severe
c. Itchiı	ng									
0	1	2	3	4	5	6	7	8	9	10
\bigcirc	0	0	0	0	0	0	0	0	0	\bigcirc
None		 		I		J.			J	Severe
d Dizz	viness									
0	1	2	3	Δ	5	6	7	0	0	10
			5		5	0	, 	0	3	
None										Severe
	the last 24	hours hou	complete	hacvour	nain raliaf	hoon?				
Please	choose the	e one perce	entage tha	t best sho	ws how mi	uch relief y	ou have re	ceived fror	n all of you	ır pain
treatm	ents comb	ined (medi	cine and n	on-medic	ine treatm	ents).				I
0%	10%	20%	30%	40%	50%	60%	70%	80%	90%	100%
0	\bigcirc	\bigcirc	\bigcirc	\bigcirc	\bigcirc	\bigcirc	0	\bigcirc	0	\bigcirc
No Relie	f									Complete Relief

Sul	oject	ID

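### The Aim 6 low-score rule for finding pain care that needs improvement points the wrong way for survey items P1-P6, where 0 is the best answer

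*Protocol*

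**What the plan says.** The prospective part of section 4.6.1.7 assesses satisfaction through the single question P9 and through "the individual items of the pain questionnaire (P1-P8 and P10-12). These outcomes will be" summarised by frequencies, means and standard deviations. The same paragraph then gives the rule: "Aspects of care with low scores or a large standard deviation will be identified as practices" needing overall improvement. No item is exempted, and neither a direction per item nor recoding is mentioned. A later sentence sends P6 back to the same descriptive treatment.

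Appendix F holds the survey. P4, for example, reads "Choose the one number below that best describes how much pain interfered or prevented you from" and runs from no interference at 0 to complete interference at 10. P7 asks about relief and ends at "Complete Relief" for 100%.

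Two other places bear on direction. Section 2.7 says that a low "pain score (little reported pain) did not guarantee that patients were satisfied with their care", so it takes a low pain score to mean little pain. The regression paragraph of 4.6.1.7 groups the items without regard to direction: the predictors "tested will include the pain relief variables (P1-P7), participation in decisions about pain treatment" and others.

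**The concern.** The rule assumes that low always means poor. That suits a satisfaction or relief score. It does not suit a score for pain, interference, distress or side effects, where low means the donor is doing well.

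Section 3.6.1 makes it an objective to measure the quality of postoperative pain management and to find where it should improve. This rule is the step in the analysis plan that produces that list. An analyst who applies it as written would list well-controlled symptoms as needing improvement, and the low-score criterion would leave out items on which donors consistently do badly.

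**Working it through.** The plan gives no figure for this rule, so there is none to reproduce. The check sets the rule beside the anchors printed in Appendix F.

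| Item | Content | Answer 0 means | Top of scale means | Low score is |
|---|---|---|---|---|
| P1, P1A, P2 | least and worst pain | no pain | worst possible (10) | good |
| P3 | share of time in severe pain | never | always (100%) | good |
| P4a-d | interference with activity and sleep | none | complete (10) | good |
| P5a-d | anxious, depressed, frightened, helpless | not at all | extremely (10) | good |
| P6a-d | nausea, drowsiness, itching, dizziness | none | severe (10) | good |
| P7 | pain relief | no relief | complete (100%) | bad |

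The low-score criterion therefore points the wrong way for every P1-P6 scale and the right way for P7. The copy of Appendix F at hand ends at P7, so the anchors of P8-P12 could not be checked; the point does not depend on them.

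**Illustration on one 0-10 item from P1-P6.** The means are assumed. The plan sets no cut-off for low; any cut-off between 1 and 9 gives the same result.

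- Mean 1 (well controlled): flagged as low. Reverse-scored, 10 − 1 = 9: not flagged.
- Mean 9 (badly controlled): not flagged as low. Reverse-scored, 10 − 9 = 1: flagged.

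**Can the standard deviation criterion correct the direction?** The standard deviation of 10 − x equals that of x, so it carries no direction. For a 0-10 item with mean m, the largest possible value is √(m(10 − m)); a binomial-type spread with p = m/10 gives √(10p(1 − p)).

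- Mean 1: maximum √(1 × 9) = 3.0; binomial-type √(10 × 0.1 × 0.9) = 0.95.
- Mean 9: maximum √(9 × 1) = 3.0; binomial-type √(10 × 0.9 × 0.1) = 0.95.

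The good and the bad item have the same range of possible spread. A poor item with scattered answers can be flagged by its standard deviation; one on which nearly all donors answer badly need not be.

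**Scale of P3 and P7.** Both offer eleven boxes from 0% to 100% in steps of 10. If these are stored as 0-100, a given relative spread has a standard deviation 10 times that of a 0-10 item, because SD(10x) = 10 × SD(x). If they are stored as 0-10, there is no difference. The protocol does not say which.

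**Planning figures in 4.6.1.6.** These do not bear on direction but were checked. With 30 donors in each of two centres and a difference of 1.7, and taking the stated SD of 2.0 to apply here too, power is 0.899 by t-test (stated 90%). With n = 200 and SD 2.0, the probability of a confidence interval half-width of at most 0.30 is 0.936 (stated 93%). Both reproduce.

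**The case against.** The strongest reply is that low is shorthand for unfavourable. The paragraph opens on satisfaction, and the sentence speaks of aspects of care and practices. Those words suit participation in decisions (P8), information received (P10) and non-medicine methods (P11, P12) better than nausea or anxiety. Section 2.7 shows that the authors know which way a pain score runs, and no sensible analyst would report low nausea as a failing. The sentence has no cut-off and no test, and it sits among histograms and boxplots. Item coding is commonly left to an analysis plan or data dictionary, and section 6.5 places data element definitions and a code list in the Manual of Operations. Item means will be presented, so a reader could see the direction.

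Much of this stands as to intent and consequence. It does not remove the error. The outcome list immediately before the rule names P1-P6 without exemption, so this is a stated rule that is wrong for items it covers, rather than a detail left for later. An analysis plan that followed it would repeat the error, and one that reversed it would depart from the protocol.

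The objection does succeed against several stronger readings:

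- A reader might infer that the rule always passes the worst items. It does not: a large standard deviation is enough to be flagged.
- A reader might count 16 of the 17 entries shown (P1, P1A, P2, P3 and four each under P4, P5 and P6, against P7) and conclude that almost the whole survey is misdirected. That denominator leaves out P8-P12 only because the available copy stops at P7.
- A reader might infer that P3 and P7 will nearly always show the largest spread. That requires storage as 0-100 and comparison in raw units, and the protocol states neither.
- A reader might want the standard deviation criterion replaced by between-centre variation. That is a preference: spread among patients is relevant to overall improvement, and the next sentence already plans boxplots and analysis of variance by centre.

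**Conclusion.** The point holds for the low-score criterion as written. Its direction is wrong for every P1-P6 scale and right for P7. Read literally, it flags well-controlled aspects and does not flag consistently poor ones, while the standard deviation criterion may still catch poor items with widely spread answers.

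The effect is confined to the descriptive list of practices needing improvement. Sample size, power and the by-centre analysis of variance are untouched. In the regression on P9, item direction changes only the sign of a coefficient.

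The conclusion rests on the printed anchors for P1-P7 and on the absence of any recoding statement in section 4.6.1.7 or in the visible part of Appendix F. How many items would actually be misclassified cannot be stated, because no cut-off is given and the means are unknown.

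**What to change.** In section 4.6.1.7, write unfavourable scores in place of low scores and state the unfavourable direction per item: high for P1-P6, low for P7 and for the satisfaction item P9. Set P8 and P10-P12 from their own anchors, and confirm P9 against its anchors at the same time. Alternatively, reverse-score P1-P6 (10 minus the answer, or 100 minus the percentage for P3) before applying the rule.

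If standard deviations are to be compared across items, put P3 and P7 on 0-10 first. Keep the standard deviation criterion and the planned analysis of variance by centre.

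The cost is a short text change and, if that route is taken, a recode. No new data are needed and the sample size does not change.
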